## **8. DISPOSITION, DEMOGRAPHICS, BASELINE CHARACTERISTICS AND MEDICAL HISTORY**

### **8.1. Disposition of Subjects**

A listing will be provided including the analysis population, first and last dose date, and the dates of and the primary reasons for the end of study treatment and end of study.

### **8.2. Protocol Deviations**

Protocol deviations will be documented by the clinical research associates and project manager on an ongoing basis throughout the study. Protocol deviations will be collected separately from (ie, external to) the eCRF database, and will be listed and discussed in the clinical study report.

### **8.3. Demographics and Baseline Characteristics**

The baseline and demographic characteristics will be listed for each subject. It will include age, sex, race, ethnicity, reproductive history, height, weight, and BMI.

### **8.4. Medical History**

General medical history will be listed including system organ class, preferred term, and start and end dates. Medical history will be coded according to the Medical Dictionary for Regulatory Activities (MedDRA) version 24.0 or higher.

Initial diagnosis and prior disease-specific therapies will be listed separately.

## **9. TREATMENTS AND MEDICATIONS**

### **9.1. Prior and Concomitant Medications**

Prior medications are defined as medications that stopped before the date and time of the first dose; concomitant medications are defined as medications that are ongoing at the first dose or start after the first dose.

### **9.2. Extent of Exposure to Investigational Drug**

Extent of exposure is defined as the total number of days a subject is exposed to investigational drug. Specifically, the duration will be calculated as (Date of Last Dose – Date of First Dose + 1).

### **9.3. Investigational Drug Compliance and Dose Intensity**

Investigational drug compliance will be calculated for each subject by taking into account whether a subject takes all doses of investigational drug as prescribed. The overall investigational drug compliance rate will be calculated as (the total number of doses administered / the total number of doses planned)  $\times 100$ . The total number of doses planned is the total number of scheduled doses until the subject's last dose.

Relative dose intensity will be calculated as (the cumulative amount of study drug administered / the cumulative planned amount of study drug).

## 10. EFFICACY ANALYSES

Efficacy analyses will be based on the RECIST 1.1 tumor assessment. Due to the small sample size, only listings will be generated.

### **Best Overall Response**

The best overall response is the best response recorded from the start of the study treatment until the end of treatment.

### **Duration of Response**

The duration of response will be calculated from the time of initial response (PR or better) to the first documentation of relapse (recurrence after CR) or progression (after PR) or death. Patients who terminated the study without documented disease progression will be censored at the last radiological assessment date.

### **Time to Initial Response**

Time to initial response is defined as time from first dose to initial response (PR or better).

### **Time to Best Overall Response**

Time to best overall response is defined as time from first dose to best overall response. If there are multiple best overall responses, the earliest one will be taken.

### **Progression-Free Survival (PFS)**

PFS is defined as the time from the date of first dose of study treatment until the date of progressive disease or death, whichever is earlier. Subjects who end the study without documented progression will be censored.

**Table 1: PFS Censoring Rules**

Situation	Date of Progression or Censoring	Outcome
No baseline tumor assessments	First Dosing visit (Cycle 1 Day 1)	Censored
Documented progression	Earliest of:  Date of radiological assessment showing new lesion(s) (if progression is based on new lesions); or Date of last radiological assessment of measured lesions (if progression is based on increase in sum of target lesions); or Date of last radiological assessment of nontarget lesions (if unequivocal progression occurs based on nontarget lesions)	Progressed
No progression	Date of last radiological assessment	Censored
Treatment discontinuation for undocumented progression	Date of last radiological assessment	Censored
Treatment discontinuation for toxicity or other reason	Date of last radiological assessment	Censored
New anticancer treatment started	Date of last radiological assessment	Censored
Death before first PD assessment	Date of death	Progressed
Death between adequate assessment visits	Date of death	Progressed
Death or progression after missing more than one tumor assessment visit	Date of death or progression	Progressed

PD = progressive disease; PFS = progression-free survival.

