- In Cycle 1, serum for ADA will be collected on Day -1 and predose (± 1 hour) on Days 1, 8, 15, 22, 29, and 36. In Cycles 2 and higher, serum for ADA analysis will be collected predose on Days 1, 15, 22 and 36 (± 2 days). Upon discontinuation from the study, serum for ADA will be collected at EOT (± 2 days), at 14 days post-EOT (± 2 days), and at 28 days post-EOT (± 2 days).
- Radiographic tumor evaluation will be performed by CT/MRI at baseline and at all other disease assessment time points. All studies for the baseline RECIST assessment should be performed within 14 days prior to the first dose of drug. The EOT tumor assessment will not be performed if the subject has had an assessment within the past 30 days.
- ^w The post-treatment fresh tumor biopsy should be performed between 12 and 21 days after first dose of XmAb18087.
- Subjects with a positive ADA at termination will be followed every 28 days (± 3 days) until ADA reverts to baseline or until the next intervening treatment.

Version 1.0 Page 59 of 145

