14.7. Efficacy Assessment

The objective of these analyses is to explore the effects of XmAb18087 when administered repeatedly as a single agent across a range of dose levels, in combination with pembrolizumab, and at RD for each Part of the study.

The assessment of antitumor effects of XmAb18087 will be based on response criteria defined in RECIST 1.1 (Appendix A).

The number and percentage of subjects achieving a best overall response of complete response (CR; confirmed and unconfirmed), partial response (PR; confirmed and unconfirmed), stable disease, progressive disease, and not evaluable will be presented.

Overall response rate is defined as subject's best response of PR or better. The number and percent of subjects who achieved ORR will be summarized. Two-sided exact 95% confidence intervals for the ORR will be determined using the binomial distribution. The duration of objective response will be calculated from the time of initial response (PR or better) to the first documentation of relapse (recurrence after CR) or progression (after PR).

The evaluable population defined in Section 14.4 will be used for summary of ORRs and duration of response.

Depending on the completeness of the available follow-up data, an analysis of PFS, measured relative to Day 1, will be performed based on the Kaplan-Meier method. Median time and its 95% confidence interval, as well as the 25th and 75th quartiles with their 95% confidence intervals, will be summarized. Progression will be determined using the criteria described in RECIST 1.1 (Appendix A). The date of progression is defined as the date of progression or death.

Version 1.0 Page 103 of 145

The date of censoring for subjects who end the study without documented progression will correspond to the date the last tumor assessment was performed. Subjects who terminated from study without postbaseline tumor assessment will be censored at Day 1.

Progression-free survival will be presented based on the safety population for the overall study.

The potential antitumor effects of XmAb18087 may also be evaluated in other subgroups of subjects. The specifications for these and other similar analyses will be described in the SAP and supersedes any protocol specifications.

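### Read literally, SAP Table 1 censors a living subject with no postbaseline scan before first dose, giving a negative PFS, whereas protocol 14.7 censors at Day 1

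*SAP*

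**What the plan says.** SAP section 10 sets the time origin: "PFS is defined as the time from the date of first dose of study treatment". Its text then states "Subjects who end the study without documented progression will be censored" and leaves the censoring date to Table 1.

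In Table 1 the rows that matter are:

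- "No baseline tumor assessments": censored at Cycle 1 Day 1. No other row censors at first dose.
- No progression, discontinuation for undocumented progression, discontinuation for toxicity or another reason, and new anticancer treatment: all four are censored at "Date of last radiological assessment". None limits this to scans after baseline.
- "Death before first PD assessment": an event at the date of death.

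Protocol 14.7 also censors at the last tumor assessment in general, but adds the special case: "Subjects who terminated from study without postbaseline tumor assessment will be censored at Day 1". On baseline imaging, the Table 7 footnotes in protocol 7.9 say: "All studies for the baseline RECIST assessment should be performed within 14 days prior to the first dose of drug".

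SAP 5.1, which lists changes from the protocol, drops the efficacy and PK-PD analyses in favor of listings. It says nothing about PFS censoring.

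**The concern.** A subject who stops early and alive, with a baseline scan and nothing after it, does not fit the no-baseline row. The subject falls into one of the four rows that use the last radiological assessment, and the only such assessment is the baseline scan, taken before the PFS clock starts. A time-to-event value below zero is impossible, so the table taken alone produces an invalid result for a case that can occur.

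The two documents also give different censoring dates for the same subject. A programmer working from Table 1 would depart from protocol 14.7 without any stated decision to do so.

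**Working it through.** The plan gives no figure to reproduce, so the check is date arithmetic.

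**Inputs**

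- PFS origin: date of first dose (SAP section 10).
- Baseline RECIST scan: no more than 14 days before first dose (protocol Table 7 footnote), and scheduled in the screening column, Day -28 to -2 (protocol Table 7). Together these give Day -14 to -2.
- Day numbering: a date before first dose has study day = date minus first-dose date, and there is no day 0 (SAP 5.2.1).
- First on-treatment scan: Day 40 ± 2 of Cycle 1 (protocol Table 7 and section 12).
- Early stop: end-of-treatment (EOT) assessments, which include a RECIST scan, are done on the day of termination (protocol 7.9.3.3 and Table 7). However, "The EOT tumor assessment will not be performed if the subject has had an assessment within the past 30 days".

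**Step 1: PFS under Table 1 read literally.** PFS = censoring date minus first-dose date. SAP section 10 gives no day-count formula for PFS, so both conventions are shown.

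**Step 2: can the case arise without a protocol deviation?** A baseline scan can count as the recent assessment that waives the EOT scan. The waiver runs to 30 days after the scan. For a Day -14 scan that is -14 + 30 = 16 days after first dose, which is study day 17. For a Day -2 scan it is -2 + 30 = 28 days after first dose, which is study day 29.

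| Baseline scan | PFS, no added day | PFS, one day added | EOT scan may be skipped through study day |
|---|---|---|---|
| Day -14 | -14 | -13 | 17 |
| Day -7 | -7 | -6 | 24 |
| Day -2 | -2 | -1 | 29 |

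PFS is negative across the whole scheduled window under either convention. A subject who stops treatment by about study day 17 to 29, well before the Day 38 to 42 scan, can follow the protocol fully and have no postbaseline scan.

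**Step 3: the same subject under protocol 14.7.** Censoring at Day 1 gives 0 days, or 1 day if one is added. It is never negative.

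**Step 4: who is not affected.** A subject who dies without a postbaseline scan is an event at the date of death. A subject with any postbaseline scan is censored after first dose.

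**The case against.** The best answer is that the Day 1 rule already exists. SAP section 2 says the SAP supplements the protocol and is to be read with it, and SAP 5.1 declares no change to PFS censoring. Read together, protocol 14.7 can fill the gap and no negative value results. This stands as a possible reading. It is not the only one, because Table 1 is not silent on these subjects: its wording assigns them a date, and that date differs from the protocol's.

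A reader might infer that the SAP table overrides the protocol, so that the negative value is the operative rule. The documents do not establish that. The sentence in protocol 14.7 about SAP specifications superseding the protocol follows directly on the subgroup analyses and most naturally refers to them. The precedence statement in protocol 14.5 speaks of its own section, which covers subject characteristics and disposition. Precedence for PFS is left open.

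It is also fair to say that the case is narrow. The subject must be alive and must leave before the first on-treatment scan, either while the EOT scan is waived or with that scan missed. With 4 subjects listed one by one, a censoring date before first dose would be easy to see.

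The no-baseline row itself does no harm. Entry requires disease measurable by RECIST 1.1 on CT or MRI, so the row should rarely apply. That might suggest it was meant to say postbaseline, but this is a guess.

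**Conclusion.** The point holds as a defect in the wording of Table 1 and as an undeclared discrepancy with protocol 14.7. For a living subject with only a baseline scan, the literal rule gives a PFS of about -14 to -2 days (-13 to -1 with one day added), against 0 (or 1) under the protocol.

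The practical effect is small. The SAP plans listings only, for 4 subjects (2 in Part A and 2 in Part C). A reader might infer that a PFS estimate is biased or that one of the four listed values is wrong. Neither is supported: no Kaplan-Meier estimate will be produced, and nothing in the documents shows that any of the 4 subjects lacks a postbaseline scan.

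The conclusion assumes that Table 1 is applied as worded, that baseline scans are done in their scheduled window, and that the efficacy listings show a derived PFS time or censoring date.

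**What to change.** In SAP Table 1:

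1. Add a row for subjects with no postbaseline tumor assessment and no death: Cycle 1 Day 1, censored.
2. Keep the no-baseline row and the death rows as they are.
3. In the other four censoring rows, limit the last radiological assessment to postbaseline assessments.

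This restores the protocol's own rule, so SAP 5.1 needs no entry for it. The cost is one table row and a one-word qualifier in four others. No new data are needed.

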### **Overall Survival (OS)**

OS is defined as time from first dose till death from any reason. Subjects who terminate the study without documented death will be censored on the date of the last visit/contact.

## **11. SAFETY ANALYSES**

### **11.1. Adverse Events**

AEs and serious AEs will be graded according to the National Cancer Institute's Common Terminology Criteria for Adverse Events (NCI-CTCAE v5.0) (except CRS, which is graded using the American Society for Transplantation and Cellular Therapy (ASTCT) CRS Consensus Grading) and be described using the MedDRA by system organ class, preferred term, severity, and relationship to XmAb18087.

Treatment-emergent AEs (TEAEs) will be marked. TEAEs are defined as events with onset dates on or after the start of study treatment or events that are present before the first infusion of XmAb18087 and subsequently worsen in severity.

### **11.2. Deaths**

Listings will be provided to document all deaths on study, including those reported on End of Study and Long-Term Follow-Up/Survival Status eCRFs.

### **11.3. Clinical Laboratory Evaluations**

Hematology, chemistry, coagulation, viral serology, and urinalysis laboratory values at each scheduled time point will be listed. Laboratory results outside predefined normal ranges and reported as clinically significant by investigators will be flagged in the data listings.

### **11.4. Physical Examination and Eastern Cooperative Oncology Group Performance Status**

Physical examination results and Eastern Cooperative Oncology Group (ECOG) performance status results will be presented in separate data listings.

### **11.5. Vital Signs**

Observed vital signs measurements at each scheduled time point will be listed for heart rate (beats/minute), respiratory rate (breaths/minute), systolic/diastolic blood pressure (mmHg), temperature (°C), and weight (kg).

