11.8. Vital Signs

Vital signs will be assessed at as indicated in Table 7. All vital signs should be taken with the subject in the same position. On nondosing days, vital signs should be measured prior to blood sampling. The following vital signs will be measured:

- Blood pressure (systolic and diastolic [mmHg])
- Heart rate (beats per minute [bpm])
- Respiratory rate (breaths per minute)

Version 1.0 Page 95 of 145

- Body temperature (°C)
- Supine BP and heart rate recordings will be made after the study subject has been recumbent and at rest ≥ 5 minutes
- Blood oxygen saturation by pulse oximetry. Oxygen saturation levels will be captured at each vital sign collection; however, pulse oximetry monitoring must be maintained continuously throughout the entire admission or observation period for each administration of XmAb18087.

Version 1.0 Page 96 of 145

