14.6. Safety Assessment

Safety variables will include AEs, PE findings, vital signs, ECGs, and laboratory values.

The extent of exposure to XmAb18087 monotherapy, as well as exposure in combination with pembrolizumab, will be summarized by dose cohort based on the number of infusions administered and the number of treatment cycles completed, as well as the total dose received. Additional summaries of drug exposure will be provided based on the PK parameters described in Section 13. Reasons for missed infusions or early permanent discontinuation of XmAb18087 will be reported.

Summary tables and listings will be provided for all reported AESC.

Adverse events will be coded using the latest version of MedDRA. The verbatim term recorded by the Investigator will be mapped to System Organ Class (SOC) and Preferred Term using MedDRA.

Treatment-emergent AEs are defined as events with onset dates on or after the start of study treatment or events that are present before the first infusion of XmAb18087 and subsequently worsen in severity.

Adverse-event-related endpoints include the following:

- TEAEs
- Treatment-emergent SAEs (TESAEs)
- Treatment-related TEAEs (for XmAb18087 or for pembrolizumab, if they can be distinguished)
- Treatment-related TESAEs (for XmAb18087 or for pembrolizumab, if they can be distinguished)
- TEAEs by severity that are defined by NCI-CTCAE, Version 5.0
- TEAEs resulting in the permanent discontinuation of XmAb18087 and/or pembrolizumab.

All AE-related endpoints will be summarized by MedDRA SOC and preferred term. At each level of summation, subject will be counted once under the greatest severity and strongest study drug relationship. All AEs will be included in the listings.

The hematology, chemistry, and other laboratory values and change from baseline values will be summarized descriptively for each scheduled assessment time point and grouped by dosing cohort. The baseline value for each laboratory value is defined as the last assessment performed on or prior

Version 1.0 Page 102 of 145

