to the date of first dose of study treatment. The toxicity grades for laboratory tests will be based on NCI-CTCAE Version 5.0 criteria. The use of blood transfusions (platelets, RBCs) and/or growth factor support will be reported. Similar analyses will be done for chemistry tests (including liver and renal function tests). Subject listings of all laboratory data collected during the study will be presented. Laboratory values outside normal limits will be identified in the subject listings and will include flags for high and low values.

Vital sign results (blood pressure, pulse, respirations, temperature, and blood oxygen saturation by pulse oximetry) and change from baseline values will be summarized descriptively for each scheduled time point. The baseline value for each vital sign measurement is defined as the last assessment performed on or prior to the date of first dose of study treatment. Additionally, the vital signs measured immediately (within 60 minutes) before each infusion of XmAb18087; at 15, 30, and 60 minutes from the start of the infusion (± 5 minutes for each time point); immediately (within 5 minutes) before EOI; at 15, 30, and 60 minutes after the EOI (± 5 minutes for each time point); and then hourly (± 5 minutes) for 3 hours postinfusion will be summarized. The change of vital signs values from preinfusion will be summarized for each postinfusion point. Preinfusion assessments are defined as last vital assessment prior to the same infusion. Subject listings of all vital data collected during the study will be presented.

Electrocardiogram values and change from baseline values will be summarized descriptively for each scheduled time point. Subject listings of all ECG data collected during the study will be presented.

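### As specified, the SAP safety listings will not show oxygen saturation or identify AESC, although protocol 14.6 commits to listing both and SAP 5.1 declares neither omission

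*SAP*

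**What the plan says.** **Vital signs.** Protocol 11.8 includes pulse oximetry among the vital signs and adds: "Oxygen saturation levels will be captured at each vital sign collection". Protocol 14.6 carries it into reporting, where the parameters are "Vital sign results (blood pressure, pulse, respirations, temperature, and blood oxygen saturation by pulse oximetry", and then commits to a listing: "Subject listings of all vital data collected during the study will be presented". SAP 11.5 begins "Observed vital signs measurements at each scheduled time point will be listed for heart rate (beats/minute" and completes the list with "respiratory rate (breaths/minute), systolic/diastolic blood pressure (mmHg), temperature (°C), and weight (kg". It does not mention oxygen saturation.

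**AESC.** Protocol 14.6 states: "Summary tables and listings will be provided for all reported AESC". SAP 11.1 says that adverse events will "be described using the MedDRA by system organ class, preferred term, severity, and relationship to XmAb18087", and the only flag it names is the treatment-emergent one: "Treatment-emergent AEs (TEAEs) will be marked". The term AESC does not appear in the SAP text, including its abbreviation list.

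**Declared changes.** SAP 5.1 reports early termination with 4 subjects (2 in Part A, 2 in Part C). It restricts output to listings of demographics, baseline characteristics, safety and efficacy assessments. It says nothing about SpO2 or AESC.

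**The concern.** With summary tables gone, the listings are the whole of the safety output. Clinically significant change in vital signs is one of the primary safety endpoints (protocol 14.3.1) and is kept in SAP 3.3, and SpO2 is one of those vital signs. If SAP 11.5 is programmed as written, a vital sign that is collected throughout the study will be missing from the report.

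The same holds for AESC, which the protocol uses to define tolerability in the run-in cohorts (7.7 and 7.8). The listings will not say which events met that definition, so a reader would have to reconstruct it. Neither gap is recorded as a change from the protocol.

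**Working it through.** No figure in the plan is at issue, so the check compares the two documents item by item.

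**Step 1. Vital-sign parameters** (protocol 14.6 against SAP 11.5, counting blood pressure as one parameter)

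| Parameter | Protocol 14.6 | SAP 11.5 |
|---|---|---|
| Blood pressure | yes | yes |
| Pulse / heart rate | yes | yes |
| Respiratory rate | yes | yes |
| Temperature | yes | yes |
| SpO2 | yes | no |
| Weight | not named | yes |

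The protocol names 5 parameters and the SAP keeps 5 − 1 = 4, adding weight. The SAP list reads as closed: the ECG list in SAP 11.6 ends with an open-ended etcetera, and the one in 11.5 does not.

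**Step 2. AESC output.** Protocol 14.6 promises two outputs, tables and listings. The SAP specifies 0 of the 2. The listings-only decision accounts for the tables, so 2 − 1 = 1 output, the listing, is missing without explanation.

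**Step 3. Is the departure authorised elsewhere?** The clause giving the SAP precedence stands in protocol 14.5 (characteristics and disposition) and is limited to that section. A similar clause at the end of 14.7 concerns subgroup and similar analyses of antitumor effect. Neither sits in 14.6. Protocol 14.2 expects departures from planned analyses to be described and justified in the study report, but SAP 5.1, the place to announce them, does not mention these two.

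**Step 4. What SpO2 would add for CRS.** A footnote to protocol Table 10 says that the more severe of hypotension and hypoxia sets the CRS grade. The table itself defines the hypoxia levels by support: low-flow cannula or blow-by at Grade 2, high-flow cannula or mask at Grade 3, positive pressure at Grade 4. A saturation value therefore supports a grade without fixing it. It still has a use. Protocol 11.1.2 has the investigator record a recognised syndrome under its own name rather than symptom by symptom, so hypoxia within CRS may have no adverse-event row. The specified listings could then show a CRS grade beside blood pressure and temperature but with no oxygenation reading.

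**Step 5. Can AESC be read from what is listed?** Partly. Protocol 7.8 uses grades and durations (for example 7 days, 5 days, 72 hours). Severity is listed under SAP 11.1, recorded dates under SAP 5.2.2.1 and laboratory values under SAP 11.3. But 7.8 also excludes events clearly attributable to the malignancy or concurrent disease, and exempts some Grade 3 events that medical management controls. Those are judgements that grade and dates do not contain. In addition, protocol 11.1.2.1 records each change of severity over days as a new event, so time spent at a given grade is spread over several rows.

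**The case against.** The strongest reply is that the SAP is silent rather than contradictory. It describes itself as a supplement to the protocol, to be read together with it and the eCRFs. It keeps safety listings in general, and SpO2 is still collected. Protocol 14.6 has not been withdrawn, so a programmer reading both documents could add the missing items. This stands as a limit on the wording: the output as specified will not show them, which is weaker than saying that it cannot.

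A reader might also infer that the report would lose one of the two determinants of CRS grade, or that the CRS primary endpoint is compromised. The documents do not support that. Table 10 grades hypoxia by oxygen support, CRS grade itself is listed under SAP 11.1, blood pressure and temperature remain in 11.5, and a hypoxia event recorded separately would still appear.

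On AESC, it is fair to say that it is not an endpoint in either document and that its main uses have lapsed. Protocol 7.7 starts each run-in cohort with 3 subjects. Parts A and C each enrolled 2, so no planned cohort-level conclusion depends on the flag. A reader might conclude that AESC status is unrecoverable, but for 4 subjects most criteria in 7.8 can be checked from the listed grades, dates and laboratory values. What remains is that the listing commitment in 14.6 does not depend on cohort size, and that attribution and management still need someone's judgement.

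**Conclusion.** The discrepancy is real and minor. Followed as written, the SAP omits 1 of 5 protocol vital-sign parameters and any AESC identification for all 4 subjects, against explicit commitments in protocol 14.6, and SAP 5.1 declares neither omission. The SpO2 gap touches a primary safety endpoint (clinically significant changes in vital signs) and removes supporting data for CRS grade, but not the grade itself. The AESC gap leaves readers to approximate a classification that also depends on attribution and management judgements.

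This assumes that the listings will be produced from the SAP text as it stands. It also assumes that SpO2 was recorded as protocol 11.8 requires. The eCRF is not among the documents, so whether AESC is a recorded field is unknown.

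**What to change.** Add SpO2 (%) to the parameters in SAP 11.5. Add an AESC yes/no flag to the adverse-event listing in SAP 11.1, or a separate AESC listing. If the sponsor prefers to leave either out, state and justify that in SAP 5.1.

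The SpO2 column costs almost nothing, since the protocol already requires the values to be captured. The AESC item may cost a little more. The adverse-event details named in protocol 11.1.2 do not include AESC status, so if the eCRF has no such field the flag will need a derivation or a brief medical review against protocol 7.8. For 4 subjects that is a small task.
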